14.4 Vector DNA Analysis

Whole blood for detection of vector DNA by PCR assay will be obtained at the baseline visit and at 1, 7 and 14 days after study agent administration.

A summary table and a subject listing will be provided for the vector analysis.

14.5 Slit-Lamp Biomicroscopy Examination

A dilated slit-lamp examination will be performed using the investigator's standard procedure. Documentation will include the presence or absence of central and peripheral schisis.

08 August 2017

A slit-lamp biomicroscopy examination of the cornea, conjunctiva, anterior chamber, iris, lens, and vitreous will be performed at each visit.

Shifts from baseline to worst value during follow-up will be tabulated. A subject listing of the slit-lamp biomicroscopy parameters will also be produced.

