#### 1.1.4.3.2. Safety and biodistribution in cynomolgus macaques

In the nonhuman primate study, three groups of male macaques (n = 6 per group) each received an intravitreal injection of 110  $\mu$ L containing rAAV2tYF-CB-hRS1 at a concentration of 3.6 x 10^11 vg/mL (4 x 10^10 vg per eye) or 3.6 x 10^12 vg/mL (4 x 10^11 vg per eye) or 110  $\mu$ L of vehicle control. Half the animals were sacrificed 14 days after vector administration and the remaining animals were sacrificed 90 days after vector administration.

The intravitreal injection procedure was well tolerated in all groups. Ocular exams demonstrated varying levels of inflammation over time.

In the vehicle control group, aqueous cells ranged from trace to 4+ at 1 week after injection and resolved by Week 2. Vitreous cells ranged from trace to 2+ at 2 to 3 weeks after injection, resolved by Week 4 in four animals and in the other two animals were resolved or resolving at Week 12. None of the animals in this group had vitreous haze.

Ocular inflammation was greater in the vector-treated animals and was more pronounced at the higher dose. Aqueous cells ranged from 1+ to 4+ at Week 1 in all animals, resolved by Week 2, recurred at Week 2 to 4 in two animals in the low dose and three animals in the high dose group, and then resolved over the next several weeks. Vitreous cells developed in 5 of 6 animals in the low dose and all animals in the high dose group, and persisted at 2+ or greater for more than 4 weeks in two animals in the low dose and three animals in the high dose group. Vitreous haze developed at Week 4 in one animal in the low dose and three animals in the high dose group.

The frequency, magnitude and time course of ocular inflammation at doses of  $4 \times 10^{10}$  and  $4 \times 10^{11}$  vg/eye in this study was similar to that seen in a toxicology study of an AAV2 vector expressing a vascular endothelial growth factor receptor inhibitor delivered by intravitreal injection at a dose of  $2.4 \times 10^{10}$  vg/eye [56]. When that product was evaluated by intravitreal injection in a human clinical trial, ocular inflammation developed in 1 of 11 subjects who received the  $2.4 \times 10^{10}$  vg dose, which was treated with topical steroids for 5 weeks during which time it resolved [57].

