### 6.9 **Ophthalmic Examinations**

Ophthalmic examinations of both eyes will be performed at the screening and baseline visits and at each visit after study agent administration, including each long-term follow-up visit. These examinations will include slit lamp examination, tonometry, indirect ophthalmoscopy and retinal biomicroscopy. Signs of inflammatory responses will be quantified using a standard 0 to 4+ cells and flare grading system [59]. On the visit at which the study agent is administered, IOP in the study eye will be measured about 30 minutes after study agent administration is completed.

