Table 14.3.11	Serious Adverse Events Related to Injection by System Organ Class and Preferred Term
Table 14.3.12	Ocular Treatment-Emergent Adverse Events by System Organ Class, Preferred Term, and Maximum Intensity
Table 14.3.13	Non-Ocular Treatment-Emergent Adverse Events by System Organ Class, Preferred Term, and Maximum Intensity
Table 14.4.1.1	Hematology Results by Group and Visit
Table 14.4.1.2	Hematology Shifts from Baseline
Table 14.4.2.1	Chemistry Results by Group and Visit
Table 14.4.2.2	Chemistry Shifts from Baseline
Table 14.4.3	Coagulation Results by Group
Table 14.4.4	Immunology Results by Group and Visit
Table 14.4.5	Slit Lamp Examination – Shift Table
Table 14.4.6	Tonometry
Table 14.4.7	Indirect Ophthalmoscopy – Shift Table

23. Listings

Listing Number	Title
Listing 16.2.1.1	Subject Disposition –Treated Subjects
Listing 16.2.1.2	Subject Disposition – Screen Failed Subjects
Listing 16.2.2	Protocol Deviations
Listing 16.2.3	Inclusion/Exclusion Criteria Violations

08 August 2017

Listing Number	Title
Listing 16.2.4.1	Demographics
Listing 16.2.4.2.1	Physical Examination Abnormalities at Baseline
Listing 16.2.4.2.2	Physical Examination Abnormalities occurring During the Study
Listing 16.2.4.3	Vital Signs
Listing 16.2.4.4	Medical History
Listing 16.2.4.5.1	Concomitant Medications
Listing 16.2.4.5.2	Carbonic Anhydrase Inhibitor Use
Listing 16.2.5	Study Agent Administration
Listing 16.2.6.1	Best-corrected Visual Acuity
Listing 16.2.6.2	Spectral Domain Optical Coherence Tomography
Listing 16.2.6.3	Static Perimetry
Listing 16.2.6.4	Kinetic Perimetry
Listing 16.2.6.5	Microperimetry
Listing 16.2.6.6.1	Reading Speed (Part 1)
Listing 16.2.6.6.2	Reading Speed (Part 2)
Listing 16.2.6.7	Contrast Sensitivity
Listing 16.2.6.8	Full-field Electroretinography
Listing 16.2.6.9	Multi-focal Electroretinography
Listing 16.2.6.10.1	25-Question Visual Function Questionnaire (VFQ-25) – Overall and SuB-Scale Scores

Listing Number	Title
Listing 16.2.6.10.2	25-Question Visual Function Questionnaire (VFQ-25) – Categorical Responses
Listing 16.2.6.10.3	Functional Vision Questionnaire for Children and Young People (FVQ_CYP)
Listing 16.2.6.11	Fundus Photography
Listing 16.2.7.1	Adverse Events by System Organ Class and Preferred Term
Listing 16.2.7.2	Serious Adverse Events
Listing 16.2.7.3	Adverse Events Leading to Early Termination
Listing 16.2.7.4	Adverse Events of Dose Limiting Toxicity (DLT)
Listing 16.2.8.1	Hematology Results
Listing 16.2.8.2	Chemistry Results

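### The eye-examination tables keep one worst grade over up to five years, so they cannot show whether ocular inflammation was early, persistent or recurrent at each dose

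*SAP*

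**What the plan says.** SAP 14.5 covers cornea, conjunctiva, anterior chamber, iris, lens and vitreous at each visit. Its summary rule is "Shifts from baseline to worst value during follow-up will be tabulated". SAP 14.7 applies the same rule to indirect ophthalmoscopy, which includes the vitreous. The table list in SAP section 22 has one entry for each examination. Table 14.4.5 is "Slit Lamp Examination – Shift Table", and Table 14.4.7 is the ophthalmoscopy counterpart. Neither section names a time window or says which grade categories form the shift.

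The grades are collected on a finer scale. Protocol 6.9 says: "Signs of inflammatory responses will be quantified using a standard 0 to 4+ cells and flare grading system". Protocol 7.2 makes these examinations the principal means of detecting ocular adverse events.

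Other safety data keep their timing. SAP 14.2.1 summarizes laboratory values by visit and tabulates shifts to each post-baseline visit. SAP 14.3 and 14.6 summarize immunology and intraocular pressure by visit. SAP 9.4 provides listings by group, subject and visit, and leaves unscheduled visits out of summaries.

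**The concern.** Safety is the primary objective. Ocular inflammation in the first 12 participants is the reason the protocol gives for treating children first at the middle dose in Group 2A. Three features of inflammation matter when doses are compared: when it occurs, how long it lasts, and whether it returns after clearing. A worst-ever grade carries none of them. The protocol's own primate data suggest that timing is part of what separates a reaction to the injection from a reaction to the vector. A table that discards timing could therefore blur the dose comparison it is meant to support.

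**Working it through.** The plan states no figure for this point, so there is none to reproduce. The check applies the worst-value rule to the protocol's primate data.

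**1. How much is collapsed.** By the visit schedule, full examinations after treatment fall on Day 1, 7 and 14, Months 1, 2, 3, 6, 9 and 12, and Years 2 to 5. That is 9 + 4 = 13 scheduled examinations reduced to one value. Day 0 requires tonometry only.

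**2. The primate data (Protocol 1.1.4.3.2).** For vehicle: "In the vehicle control group, aqueous cells ranged from trace to 4+ at 1 week after injection and resolved by Week 2". For vector: "Aqueous cells ranged from 1+ to 4+ at Week 1 in all animals", which then cleared and "recurred at Week 2 to 4 in two animals in the low dose and three animals in the high dose group". For vehicle vitreous cells: "Vitreous cells ranged from trace to 2+ at 2 to 3 weeks after injection".

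| Finding | Vehicle | Low dose | High dose | Visible in a worst-value table? |
|---|---|---|---|---|
| Aqueous cells, Week 1 | trace to 4+ | 1+ to 4+ (range for both doses) | 1+ to 4+ (range for both doses) | Grade yes, date no |
| Aqueous recurrence, Weeks 2 to 4 | none reported | 2 animals | 3 animals | No |
| Vitreous cells at 2+ or more beyond 4 weeks | none reported | 2 animals | 3 animals | Grade yes, duration no |
| Vitreous haze | 0 | 1 animal | 3 animals | Yes, if haze is tabulated |

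The 0, 2, 3 ordering for aqueous recurrence appears only when the data are split by time. If the shift were coded simply normal or abnormal, every vector animal (6 + 6 = 12) would already be abnormal at Week 1, and later events could add nothing.

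**3. The masking rule.** Let E be the early grade and L the later grade. The table reports W = max(E, L). If E is at least L, then W = E and the later event leaves no trace. If E is below L, then W = L, but the table cannot show that it came later. An eye that reached 4+ early cannot register a later rise, because 4+ is the top of the scale.

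The chance that a later grade is hidden is P(E ≥ L). The documents give ranges, not a distribution of early grades, so the distributions below are assumptions. They apply to eyes with some early reaction and take E and L as independent.

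| Assumed share at trace / 1+ / 2+ / 3+ / 4+ | L = 1+ | L = 2+ | L = 3+ | L = 4+ |
|---|---|---|---|---|
| 40 / 30 / 15 / 10 / 5% | 60% | 30% | 15% | 5% |
| 20% each | 80% | 60% | 40% | 20% |
| 5 / 10 / 15 / 30 / 40% | 95% | 85% | 70% | 40% |

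For L = 2+, the three sums are 15 + 10 + 5 = 30%, 20 + 20 + 20 = 60%, and 15 + 30 + 40 = 85%. An eye with no early cells masks nothing.

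**4. Denominators.** The primate groups had 6 animals each and half were sacrificed at Day 14, which leaves 3 per group. Yet the account of vehicle vitreous cells follows 4 + 2 = 6 animals to Week 4 or Week 12. The number at risk after Day 14 is therefore unclear, so only counts are used here, without proportions or tests.

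**5. Whether another table fills the gap.** Under SAP 14.1, adverse-event tables count each preferred term once per participant, and the intensity tables use the maximum intensity. No onset window is given. Fundus photography (SAP 15.9) includes an inflammation item by visit, but only at baseline and Month 12. The listings hold grades by visit, but they are not summaries by dose.

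**The case against.** The strongest reply is that nothing is lost from the data. With 3 participants in each adult escalation group, the by-visit listings let a reader follow each eye. Ocular adverse events are tabulated separately by relationship to the study agent and to the injection procedure, which bears directly on the question of vector or injection. Protocol 7.3.1 records onset and resolution dates. Data and Safety Monitoring Committee reviews draw on a summary of all available data.

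Much of this stands: the defect lies in the tables and not in data capture. It does not remove the point. The relationship tables rest on investigator judgement in an open-label trial and carry no timing. Group 2A (up to 6) and Group 4 (up to 15) are larger to follow through listings. No planned table gives examined grade by dose over time.

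The objection also rules out several stronger readings that a reader might infer:

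- *The Week 1 reaction sets the worst value in general.* The 4+ with vehicle is aqueous cells only. Vehicle vitreous cells came later and reached 2+, and Protocol 1.2.2 puts maximal inflammation in vector animals at 4 weeks.
- *All late inflammation is specific to vector.* In two vehicle animals, vitreous cells were resolved or still resolving at Week 12.
- *Dose groups would look alike on worst grade.* The protocol gives ranges without counts per grade, and says inflammation was greater with vector and at the higher dose.
- *Haze would be hidden.* A worst-value table of haze would return 0, 1 and 3.
- *A subconjunctival hemorrhage would mask intraocular cells.* Conjunctiva is examined separately from anterior chamber and vitreous.

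**Conclusion.** The concern holds in a limited form. SAP 14.5 and 14.7 summarize examined inflammation only by its worst value, and no other planned table shows its course by dose. For anterior chamber cells, an early injection reaction can mask a later recurrence; in the primates, recurrence was reported in 2 low-dose and 3 high-dose animals and in none given vehicle. For vitreous cells, the main loss is duration; persistence at 2+ or more beyond 4 weeks was reported in 2 low-dose and 3 high-dose animals. For 14.7, only the vitreous is at issue, because that examination has no anterior chamber component.

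The size in participants is unknown. The 30% to 85% range for a later 2+ depends entirely on assumed early grades. Carry-over from the primates is itself an assumption: they received 110 µL in an eye of about 2.5 mL, whereas participants receive 70 or 140 µL in an eye of about 5 mL. Participants may also receive prophylactic steroids, and the trial has no vehicle-injected eye. The documents do not support a prediction that the human tables will mislead. They do show that the tables as planned cannot answer the question.

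**What to change.** In SAP 14.5, and for the vitreous in 14.7:

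- Add a descriptive table of study-eye anterior chamber and vitreous cell, flare and haze grades, by group or dose and scheduled visit. Shifts in pre-set early and later windows would also serve, but a by-visit table avoids choosing cut-points. A later window would not by itself isolate vector effects, since vehicle vitreous cells appeared at Weeks 2 to 3.
- Add the number of participants by dose whose inflammation is present at two or more consecutive visits, and the number in whom it recurs after clearing. Show the visits concerned, because visit spacing is unequal.
- Keep the worst-value tables, state the grade categories used, and say whether grades from unscheduled visits count toward the worst value.

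The cost is SAP wording and a few more descriptive tables with small group sizes. No new data or inference is needed. SAP section 1 already allows supplementary analyses if the study report identifies them.

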14.6 Tonometry

Tonometry will be used to measure intraocular pressure (IOP). The observed and change from baseline values for IOP will be summarized for each eye using continuous descriptive statistics by visit for each group and for all subjects.

Subject listings of tonometry results will also be produced.

14.7 Indirect Ophthalmoscopy

An indirect ophthalmoscopy examination of the vitreous, disc, macula, vessels, lens, and periphery will be performed at each visit. Shifts from baseline to worst value during follow-up will be tabulated.

Subject listings of indirect ophthalmoscopy results will also be produced.

15. Efficacy Analyses

15.1 Visual Acuity

BCVA testing will be performed once at the screening visit, twice at the baseline visit, and once at each visit after study agent administration, including each long-term follow-up visit. BCVA will be determined using a standard ETDRS visual acuity testing protocol.

The observed and change and percent change from baseline (average of the two baseline results) visual acuity will be summarized for each eye using continuous descriptive statistics by visit for each group and for all subjects. P-values from paired t-tests comparing post-baseline visits with baseline visit and p-values from 2-sample t-tests comparing study eye with fellow eye will be presented for Treatment Groups 2A, 2+2A, 4, 3+4, and all subjects combined. All inferential statistics are

exploratory in nature. Visual acuity data will be presented as the letter score and the logMAR (calculated as (85-ETDRS)/50, where ETDRS is the ETDRS/EVA letter score) at each time point. Change from baseline in ETDRS letter score will be summarized for the following categories: <=-15, -15 to <-8, -8 to <0, no change, >0 to 8, >=8 to 15, >=15. A subject listing of visual acuity will also be produced.

Box plots of change from baseline in ETDRS BCVA by visit will be presented by group and overall (one box for each group side-by-side at each visit) and repeated by eye (study eye and fellow eye).

Line plots of ETDRS BCVA letter score by visit with 95% confidence intervals (CIs) will be plotted by group and overall. Right and left eyes will be displayed side-by-side on the same page.

Histograms of ETDRS BCVA score at each visit by group and overall will be presented in panel graphs (one panel for each group by visit) and repeated by eye (study eye and fellow eye).

08 August 2017

Scatter plots of ETDRS BCVA score at follow-up visits versus baseline (also known as shift plots) by group and overall will be presented in panel graphs (one panel for each group by visit) and repeated by eye (study eye and fellow eye). A regression line and a line going through the origin will be overlaid in the scatter plots.

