9.3 Definition of Baseline and Pretreatment

Values from the baseline visit (or an average for multiple baseline values) will be considered baseline values for any variables that are analyzed over time. If baseline visit data were not collected, then screening values will be used as baseline values. Pretreatment values will be all values collected at screening or baseline visits.

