Table 14.2.1.2	Best Corrected Visual Acuity – Inferential Statistics
Table 14.2.1.3	Best Corrected Visual Acuity Letter Score - Categorical Summary
Table 14.2.2.1	Spectral Domain Optical Coherence Tomography
Table 14.2.2.2	Spectral Domain Optical Coherence Tomography – Inferential Statistics
Table 14.2.3.1.1	Static Perimetry
Table 14.2.3.1.2	Static Perimetry – Inferential Statistics
Table 14.2.3.2.1	Kinetic Perimetry
Table 14.2.3.2.2	Kinetic Perimetry – Inferential Statistics
Table 14.2.4.1	Microperimetry
Table 14.2.4.2	Microperimetry – Inferential Statistics
Table 14.2.5.1	Reading Speed
Table 14.2.5.2	Reading Speed – Inferential Statistics
Table 14.2.6.1	Contrast Sensitivity
Table 14.2.6.2	Contrast Sensitivity – Inferential Statistics
Table 14.2.7.1.1	Full-field Electroretinography
Table 14.2.7.1.2	Full-field Electroretinography – Inferential Statistics
Table 14.2.7.2.1	Multi-focal Electroretinography

Table 14.2.7.2.2	Multi-focal Electroretinography – Inferential Statistics
Table 14.2.8.1	25-Question Visual Function Questionnaire (VFQ-25)
Table 14.2.8.2	25-Question Visual Function Questionnaire (VFQ-25) – Inferential Statistics
Table 14.2.8.3	Functional Vision Questionnaire for Children and Young People (FVQ_CYP)
Table 14.2.8.4	Functional Vision Questionnaire for Children and Young People (FVQ_CYP) – Inferential Statistics
Table 14.2.9	Fundus Photography
Table 14.3.1	Overall Summary of Treatment-Emergent Adverse Events
Table 14.3.2	Ocular Treatment-Emergent Adverse Events by System Organ Class and Preferred Term
Table 14.3.3	Non-Ocular Treatment-Emergent Adverse Events by System Organ Class and Preferred Term
Table 14.3.4	Grade 3 or 4 Treatment-Emergent Adverse Events that Occurred During the 12 Months after Study Drug Administration by System Organ Class and preferred Term
Table 14.3.5	Ocular Treatment-Emergent Adverse Events Related to Study Agent by System Organ Class and Preferred Term
Table 14.3.6	Non-Ocular Treatment-Emergent Adverse Events Related to Study Agent by System Organ Class and Preferred Term
Table 14.3.7	Ocular Treatment-Emergent Adverse Events Related to Injection by System Organ Class and Preferred Term
Table 14.3.8	Non-Ocular Treatment-Emergent Adverse Events Related to Injection by System Organ Class and Preferred Term
Table 14.3.9	Serious Adverse Events by System Organ Class and Preferred Term

Table 14.3.10	Serious Adverse Events Related to Study Agent by System Organ Class and Preferred Term

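### The BCVA change classes in SAP 15.1 overlap at −15, +8 and +15 letters and treat −8 and +8 differently, so Table 14.2.1.3 cannot be programmed as written without double counting or an unstated choice

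*SAP*

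**What the plan says.** SAP 15.1 (Visual Acuity) sorts each eye's letter-score change into seven classes: "<=-15, -15 to <-8, -8 to <0, no change, >0 to 8, >=8 to 15, >=15". The output is Table 14.2.1.3, listed in SAP section 22 as "Best Corrected Visual Acuity Letter Score - Categorical Summary".

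Testing frequency and baseline are set out as follows:

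- SAP 15.1: "BCVA testing will be performed once at the screening visit, twice at the baseline visit, and once at each visit after study agent administration".
- SAP 9.3: "Values from the baseline visit (or an average for multiple baseline values) will be considered baseline values".
- SAP 9.3, fallback: "If baseline visit data were not collected, then screening values will be used as baseline values".
- SAP 15.1 repeats the averaging for this variable: "change and percent change from baseline (average of the two baseline results) visual acuity".

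SAP 9.4 defines change as follow-up minus baseline. SAP 9.3, 9.4 and 15.1 contain no rounding rule for the baseline mean, no tolerance around zero and no rule for a value that sits on a class boundary. Protocol 10.7.3 asks only for the letter score at each time point and defines no change classes, so the SAP is the only source for this table.

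**The concern.** Each eye at each visit should fall in exactly one class of a categorical change table, and a loss should be classed by the same rule as a gain of the same size. This list does neither. If it is programmed literally, some eyes are counted twice and a column can exceed 100%. If it is not, the programmer must choose a class for the boundary values and nothing in the SAP records the choice. The mismatch at 8 letters leans one way: a gain of exactly 8 can be shown in the larger class and a loss of exactly 8 cannot. In an uncontrolled open-label study with groups as small as 3, one eye in the wrong row is visible.

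**Working it through.** The documents state no count or percentage for this table, so there is no figure of the plan's own to reproduce.

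**Step 1. Class membership.** Label the seven classes A to G in the SAP's order: A is the largest loss, D is no change, G is the largest gain. B and C have an unsigned lower bound (−15 and −8). E and F have an unsigned upper bound (8 and 15). Every whole- and half-letter change from −40 to +40 was assigned under each of the four possible conventions for those bounds.

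| Unsigned lower / upper bound | Values in two classes | Values in no class | −8 | +8 |
|---|---|---|---|---|
| inclusive / inclusive (literal) | −15 (A, B); +8 (E, F); +15 (F, G) | none | C | E and F |
| inclusive / exclusive | −15 (A, B) | none | C | F |
| exclusive / inclusive | +8 (E, F); +15 (F, G) | −8 | none | E and F |
| exclusive / exclusive | none | −8 | none | F |

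No row places every value in exactly one class, and −8 and +8 are not mirrored in any row.

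**Step 2. How often an eye lands on an overlap value.** Inputs: two whole-letter baseline tests and one whole-letter follow-up test (SAP 15.1), no rounding of the mean, and an assumed SD *s* per reading of 3, 4 or 5 letters. For a stable eye the change has variance s² + s²/2, so σ = s√1.5, on a half-letter grid. To a close approximation P(change = x) = 0.5 × φ(x/σ)/σ, where φ is the standard normal density.

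| s | σ | P(+8) | P(−15) + P(+15) | Any overlap value | × 27 eyes |
|---|---|---|---|---|---|
| 3 | 3.674 | 0.51% | <0.01% | 0.51% | 0.14 |
| 4 | 4.899 | 1.07% | 0.07% | 1.15% | 0.31 |
| 5 | 6.124 | 1.39% | 0.32% | 1.71% | 0.46 |

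By symmetry P(−8) equals P(+8). In a group of 3 the expected number is 3 × 0.51% to 3 × 1.71%, that is 0.02 to 0.05 eyes per visit. With a true mean gain of 5 to 8 letters and the same SDs, simulation gives 1.0 to 1.7 of 27 eyes on an overlap value.

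**Step 3. Effect of one double-counted eye.** The column total is (n + 1)/n: 4/3 = 133.3% for n = 3 and 28/27 = 103.7% for n = 27.

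**Step 4. The exact-zero class.** If the two baseline scores have an odd sum, the mean ends in .5 and a whole-letter follow-up cannot give a change of 0. With readings modelled as rounded normal values, the probability of an odd sum is 0.47 at a per-test SD of 0.5 letters and 0.50 from 1 letter upward, so about half of eyes with two baseline tests are shut out. To see how much this matters, compare a two-test mean with a single whole-letter baseline, for which the change has SD s√2 on a whole-letter grid:

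- Two-test mean: 0.5 × 0.3989/(s√1.5) = 5.4%, 4.1%, 3.3% for s = 3, 4, 5.
- Single test: 0.3989/(s√2) = 9.4%, 7.1%, 5.6%.

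The ratio is 0.5√2/√1.5 = 0.58 in each case. Averaging therefore removes 2 to 4 percentage points from a class that would hold under 10% of stable eyes in any event.

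**The case against.** The strongest case for leaving this alone is that it is a slip in one descriptive table of a secondary variable. No dose step, decision rule or test uses the classes, and SAP 15.1 calls all its inferential statistics exploratory. The continuous summaries, plots and subject listing do not depend on the classes, so any eye can be reclassified from the listing. Boundary hits are uncommon, and a programmer would more likely pick one class than count an eye twice. All of this stands and limits the weight of the point. It does not remove the fault, because the choice would still be undocumented.

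One could also suppose that a less-than sign was lost before 8 and before 15 when the text was extracted. That is the second row of the table in Step 1: −15 is still in two classes and ±8 are still not mirrored.

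A reader might go further and infer that 95% to 97% of unchanged eyes would be mislabelled as gains or losses because baseline is averaged. The working does not support this. With a single whole-letter baseline, 91% to 94% of stable eyes would still differ from zero, so most of that figure is test-retest noise, which any exact-zero class shows. A reader might also treat this as the trial's responder analysis of its main efficacy measure. The SAP defines no responder, titles the output a categorical summary, and lists BCVA in section 3.2 among several unranked secondary variables.

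**Conclusion.** The class list is wrong as written. It is not mutually exclusive at −15, +8 and +15, and it is not symmetric at ±8. These two findings follow from the wording alone and need no assumption. The size does rest on assumptions: whole-letter scores, two baseline tests, an unrounded mean and a reading SD of 3 to 5 letters. On that basis an overlap value is expected in fewer than one of 27 stable study eyes per visit, and in one to two if there is a real gain of 5 to 8 letters.

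The exact-zero observation is secondary. About half of eyes with two baseline scores cannot reach 0, which cuts that class from about 6–9% to about 3–5% of stable eyes. Eyes with a single baseline score, or with the screening value as fallback, can still reach 0. The point warrants correcting the SAP wording, but it does not call the other BCVA analyses into question.

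**What to change.** Replace the list in SAP 15.1 with exclusive, mirrored classes at the existing cut-points, for example: ≤ −15; > −15 to ≤ −8; > −8 to < 0; 0; > 0 to < 8; ≥ 8 to < 15; ≥ 15. Each whole- or half-letter change then falls in exactly one class. Placing both −8 and +8 in the smaller-change classes would serve equally well, provided the two sides match.

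Optionally add a combined row for changes between −8 and +8 (exclusive), so that small changes are not read as gain or loss. For stable eyes it would hold about 96%, 89% and 79% at SDs of 3, 4 and 5. This row does not open the exact-zero class to eyes with a half-letter baseline. If that class is meant to represent stability, the SAP needs a stated tolerance band or a rounding rule for the baseline mean.

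The cost is one line of SAP text and the format statement for Table 14.2.1.3, with no new data. The protocol's version history mentions a 12-month analysis. If this table was already produced for it, record which boundary rule was programmed and recheck the counts against the listing.
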